Protocol Title: The Role of Highly Selective Androgen Receptor (AR) Targeted Therapy in Men with Biochemically Relapsed Hormone Sensitive Prostate Cancer

Investigator Signature *Date*

Print Name and Title

[figure not shown]
Site # _____

Site Name _____

ABSTRACT

Title	The Role of Highly Selective Androgen Receptor (AR) Targeted Therapy in Men with Biochemically Relapsed Hormone Sensitive Prostate Cancer
Study population	
Key Eligibility Criteria:
 
 • Histologically proven adenocarcinoma of the prostate • Rising PSA after prior definitive local therapy (radical prostatectomy, external beam radiation, or brachytherapy) or combination of radical prostatectomy and radiotherapy • Prior primary or salvage radiation or not a candidate for localized salvage radiation due to subject preference or clinical assessment based upon disease characteristics and/or subject co-morbidities. • PSA doubling time ≤ 12 months • No evidence of metastatic disease by computed tomography (CT)/magnetic resonance imaging (MRI) abdomen/pelvis and whole body bone scan. Abdominal/pelvic lymph nodes measuring less than or equal to 2 cm in short axis are allowed. • Minimum PSA 1.0 ng/mL if prior radical prostatectomy +/- adjuvant or salvage radiation; nadir + 2.0 ng/mL if prior RT without prior radical prostatectomy • No androgen deprivation therapy (ADT) within 6 months prior to randomization • No prior ADT for biochemical relapse • No 5-alpha reductase inhibitor or anti-androgen within 6 weeks prior to randomization • Prior chemotherapy is allowed only in the (neo) adjuvant setting, and if last dose was >6 months prior to randomization • Serum testosterone ≥ 150 ng/dL • No prior use of bone-modifying agent within 3 months prior to randomization • QTc interval ≤ 480 msec • No history of seizures or medical conditions, which may lower seizure threshold
Rationale for Study	
Prostate cancer patients with biochemical relapse (BCR), and a PSA doubling time (PSADT) of 12 months or lower represent a subset of patients at significant risk for the development of metastases and prostate cancer-specific mortality. In general, ADT is an appropriate approach for these patients, but carries risks of its own, including a potential impact on quality of life (QOL), and the potential for clinically significant metabolic derangements. Consequently, new strategies that can mitigate these adverse effects represent an important unmet need. Two potential strategies in this group of patients are a) to utilize a highly active second generation androgen receptor (AR) inhibitor as monotherapy and b) to add a highly active second generation AR inhibitor to conventional luteinizing hormone releasing hormone (LHRH) agonist (LHRHa) intermittent androgen deprivation (IADT). The first approach is predicated on the expectation that AR inhibitor monotherapy will have fewer adverse events, while the second approach is based on the expectation that more effective combination therapy will result in greater anti-cancer activity, and consequently, after a finite period of therapy, allow a longer period of time off ADT (and hence improved QOL) as part of an intermittent ADT approach. The proposed clinical trial will study the effects of 12 months of therapy with ARN-509 (a highly potent second generation AR antagonist) alone, or in combination with an LHRHa, each compared with LHRHa alone, in men with a rapidly rising serum PSA after prior definitive local therapy for prostate cancer. Endpoints selected reflect measurable short-term effects of ADT, including QOL and several metabolic parameters. In addition, the relative effect of each treatment strategy on PSA suppression as well as testosterone recovery (and subsequent PSA progression) after 12 months of therapy will be evaluated. Favorable results suggesting an improvement in QOL for either strategy will provide justification for larger definitive trials of second generation AR inhibitors as a treatment alternative or addition to LHRHa therapy in the BCR disease population.

Primary Objectives	
 To compare the mean change from baseline in QOL as measured by total FACT-P score over a period of 12 months of therapy with ARN-509 monotherapy vs. LHRHa monotherapy in men with BCR to test for superiority with ARN-509 monotherapy To compare the mean change from baseline in QOL as measured by total FACT-P score over a period of 12 months of therapy of ARN-509 + LHRHa vs. LHRHa monotherapy in men with BCR to test for non-inferiority with ARN-509 + LHRHa
Secondary Objectives	
 Other Quality of Life Instruments: To compare (a) ARN-509 monotherapy vs. LHRHa monotherapy and (b) ARN-509 + LHRHa vs. LHRHa monotherapy with regards to change over time in QOL To compare (a) ARN-509 monotherapy vs. LHRHa monotherapy and (b) ARN-509 + LHRHa vs. LHRHa monotherapy with regards to PSA modulation: To compare (a) ARN-509 monotherapy vs. LHRHa monotherapy and (b) ARN-509 + LHRHa vs. LHRHa monotherapy with regards to metabolic and hormonal effects: To characterize the safety profile of ARN-509 monotherapy and in combination with LHRHa. Biomarker analyses will be conducted on formalin-fixed paraffin-embedded (FFPE) blocks or slides, plasma, and whole blood samples collected from consented subjects to assess AR^{F876L} mutation and other resistance markers from all 3 treatment groups.

Study Design	
Phase 2, randomized, open-label 3-arm multicenter study evaluating 12 months of treatment with LHRHa monotherapy, ARN-509 monotherapy, or the combination in men with non-metastatic biochemically relapsed prostate cancer with rapidly rising PSA levels after prior definitive therapy for localized prostate cancer. Subjects will be stratified by PSADT (< 6 months vs. 6-12 months) and age (≤ 70 vs. > 70) and randomized with equal probability from within each of the 4 strata to 1 of the 3 study arms. There will be 2 periods of 12 months each in the 24 month-long treatment period: (1) an On-therapy Period lasting 12 months, during which time subjects receive randomly assigned protocol therapy, and (2) an Off-therapy Observation Period also lasting 12 months.
  
N = 30 patients per arm
 
Study Treatment Period = 24 months
 
 "On Therapy" Period* 12 months 
 
 "Off Therapy" Observation Period* 12 months 
 
 Randomize Stratified by PSADT (less than 6 months vs. 6 – 12 months) and age (≤ 70 vs. > 70) 
 
 ARN-509 LHRH agonist + ARN-509 LHRH agonist 
 
 Observation Observation Observation 
 
Followup†
 
*Patients with PSA or radiographic progression will discontinue protocol treatment and will be treated as per individual investigator discretion
 
† Patients will be followed until the time of PSA or radiographic progression, or initiation of non-protocol therapy, whichever happens first

Number of subjects	Ninety men, with a rising serum PSA after prior definitive therapy including radical prostatectomy and/or radiation therapy, who have a PSADT of less than or equal to 12 months, will be enrolled.
Duration of Therapy	Subjects will receive protocol therapy for a maximum of 12 months, or shorter duration if evidence of PSA/radiographic progression or unacceptable toxicity during protocol therapy or subject/physician withdrawal from the study. If there is no evidence of disease progression after 12 months of protocol therapy, subjects will enter the therapy Off-therapy Observation period (Months 13-24).
Duration of Follow up	If there is no evidence of PSA or radiographic progression after 24 months from Day 1 of the On-Treatment Period, subjects will enter a Follow-up Period. Subjects will remain on study until the time of PSA or radiographic progression or initiation of non-protocol therapy or subject/physician withdrawal from the study, whichever occurs first. Subjects in the Follow-up Period will be discontinued at the time of the final clinical cutoff described in the following section.
Duration of study	With estimated accrual duration of 12 months, the data-cutoff for analysis of primary and secondary endpoints will be at 36 months from the time the study opens to accrual. The Sponsor will establish a final clinical cutoff date after all subjects have completed the Month 24 Visit. Data collection will cease at this time. The final clinical study report will be written based on these data. The total study duration is 6 years; the last patient was consented at 4 years and the final clinical cutoff is 2 years (24 months) after last patient was consented.

Study Drugs	
1. ARN-509 With Amendment 7 (Version 8.0), subjects receiving the softgel capsules will switch to tablets starting at the next cycle and all newly enrolled subjects will receive tablets. Drug Substance: ARN-509 drug substance is an almost white to slightly brown powder. Formulation: The ARN-509 tablet supplied for this study contains 60 mg of JNJ-56021927. It will be manufactured and provided under the responsibility of the Sponsor. Dose and Route of Administration: ARN-509 will be administered orally on a continuous daily dosing regimen at a dose of 240 mg per day (4 x 60-mg tablets) with or without food.
 
2. LHRH Agonist Choice of specific LHRHa to be used in this study will be per investigator discretion/site practice guidelines. Options include Eligard®, Lupron Depot®, Zoladex®, or Trelstar®. Dosing schedule will be per individual investigator discretion. The use of LHRH antagonists (e.g. degarelix) will not be permitted. Route of Administration: The LHRHa injections will be delivered either subcutaneously (Eligard®, Zoladex®) or intramuscularly (Lupron Depot®, Trelstar®) by a trained health care provider while on protocol therapy.

Safety Assessments	
Safety Assessments: During each monthly study visit during protocol therapy, the maximum grade observed for each toxicity will be tabulated, as graded by National Cancer Institute (NCI)-Common Terminology Criteria for Adverse Events (CTCAE) Version 4.03. Interim Safety Review: Will be performed after 20 subjects have completed at least 1 month of therapy with either ARN-509 monotherapy or ARN-509 + LHRHa. If there are > 5 subjects with Grade 3 or higher toxicities not typically related to ADT, that the study investigator deems as possibly, probably, or definitely treatment-related, the study will be terminated. Study accrual will continue during the interim safety review.

Study Endpoints	
Primary Endpoint: Mean change from baseline in total FACT-P score at 12 months Secondary Endpoints: Additional Quality of Life Measures:
 
 • Mean change from baseline in total FACT-P, EORTC QLQ-C30/PR25, and SHIM scores over time 
PSA Modulation:
 
 • Time to PSA progression • Proportion of subjects without PSA or radiographic progression and recovery of serum testosterone to > 150 ng/dL at 24 months. • Proportion of subjects with a serum PSA < 0.2 ng/mL after 7 months of protocol therapy 
Metabolic and Hormonal:
 
 • Mean change from baseline in markers of insulin resistance (BMI, fasting glucose/insulin, hemoglobin A1C), fasting lipids, bone mineral density (as measured by DEXA at the femoral neck, and lumbar spine) over time • Time to testosterone recovery to > 50 ng/dL and > 150 ng/dL during the Off-therapy Observation Period • Mean change from baseline in serum DHT and estradiol levels over time 
Safety:
 
 • Incidence and severity of adverse events • Abnormal findings in physical exams and laboratory tests 
Correlative studies
 
 • Frequency of subjects emerging with ARF876L mutation at the end of treatment and progression. • Frequency of subjects expressing various RNA markers previously demonstrated to confer resistance ARN-509 at baseline, end of treatment, and progression

Unique Aspects of the Study	This study represents the first clinical trial investigating the use of ARN-509, a potent, second generation AR antagonist in a hormone-sensitive prostate cancer disease population. Furthermore, the study endpoints, including QOL and changes in metabolic markers represent clinically relevant, measurable study endpoints, which can be utilized in initial Phase 2 randomized trials comparing novel treatment paradigms vs. standard ADT in biochemically relapsed disease as a means of justifying the further study of a novel agent in this disease setting.
------------------------------------	--

List of Abbreviations

ADT	androgen deprivation therapy
AlkP	alkaline phosphatase
ALT	alanine aminotransferase
AR	androgen receptor
ASCO	American Society of Clinical Oncology
AST	aspartate aminotransferase
ASTRO	American Society for Therapeutic Radiology and Oncology
BCR	biochemical relapse
BMD	bone mineral density
BMI	body mass index
CAB	combined androgen blockade
CBC	complete blood count
CI	confidence interval
eCRF	electronic case report form
CRPC	castrate-resistant prostate cancer
CT	computerized tomography
CTCAE	Common Terminology Criteria for Adverse Events
DAO	data as observed
DEXA	dual energy x-ray absorptiometry
DHT	dihydrotestosterone
DLT	dose-limiting toxicity
ECOG	Eastern Cooperative Oncology Group
eDC	electronic data capture
EORTC	European Organization for Research and Treatment of Cancer
FACT-P	Functional Assessment of Cancer Therapy – Prostate
FDA	Food and Drug Administration
FFPE	formalin-fixed paraffin-embedded
HDL	high-density lipoprotein
HR	hazard ratio
IADT	intermittent androgen deprivation therapy
ITT	intent-to-treat

LDL	low-density lipoprotein
LHRH	luteinizing hormone-releasing hormone
LHRHa	LHRH agonist
MRI	magnetic resonance imaging
NCI	National Cancer Institute
NCIC	National Cancer Institute of Canada
OS	overall survival
PAB	peripheral androgen blockade
PBMC	peripheral blood mononuclear cells
PQC	product quality complaint
PSA	prostate-specific antigen
PSADT	PSA doubling time
QOL	quality of life
RT	radiation therapy
RTOG	Radiation Therapy Oncology Group
TSH	thyroid stimulating hormone
SHIM	Sexual Health Inventory for Men

Table of Contents

PROTOCOL AMENDMENTS	16
1 Background	31
1.1 Biochemically Relapsed Prostate Cancer	31
1.2 Risk Adapted Therapy for BCR Prostate Cancer	31
1.3 Therapeutic Options in BCR Prostate Cancer Patients	32
1.3.1 Combined Androgen Blockade (CAB)	32
1.3.2 Intermittent ADT (IADT)	32

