3 STUDY DESIGN

3.1 OVERALL STUDY CHARACTERISTICS

This is a Phase 2, randomized, open-label 3-arm multicenter study evaluating 12 months of treatment with an LHRHa monotherapy, ARN-509 monotherapy, or the combination in men with non-metastatic biochemically relapsed prostate cancer with rapidly increasing PSA levels after prior definitive therapy for localized prostate cancer. The two experimental arms (ARN-509 monotherapy; ARN-509 + LHRHa) will each be compared with a control arm of standard androgen deprivation (LHRHa monotherapy). Subjects will be stratified by PSADT (< 6 months vs. 6-12 months) and age (≤ 70 vs. greater than 70) and randomized with equal probability (1:1:1 ratio) from within each of the four strata to one of the 3 study arms.

There will be 2 treatment periods of 12 months each (24 months):

- (1) On-therapy Period lasting 12 months, during which time subjects receive randomly assigned protocol therapy
- (2) Off-therapy Observation Period from months 13 through 24

Subjects who develop progressive disease (either by serum PSA or radiographic progression) at any time during the 2 study periods will be removed from the study and will be treated as per individual investigator discretion. Subjects who discontinue before completion of the On-therapy Period in the absence of progressive disease will enter the Off-therapy Observation Period of the study. If subjects do not have evidence of PSA or radiographic progression at the end of 24 months, they will remain on study, enter a Follow-up Period, and be followed until PSA or radiographic progression or initiation of non-protocol therapy. Non-protocol therapy is defined as re-initiation of hormonal therapy or initiation of other anti-cancer therapy. The total study duration is 6 years from the date of first subject enrolled once the Off-therapy Observation Period has been completed. Subjects in the Follow-up Period will be discontinued at the time of the final clinical cutoff as described in Section 11.2.2.

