3.4 STUDY TIMELINES

3.4.1 Primary Completion:

With estimated accrual duration of 12 months, the data-cutoff for analysis of primary and secondary endpoints will be at 36 months from the time the study opens to accrual.

3.4.2 Study Completion:

The study is estimated to reach completion 5 years from the time the study opens to accrual.

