11.2.2 Final Clinical Cutoff

The Sponsor will establish a final clinical cutoff date after all subjects have completed the Month 24 Visit. Data collection will cease at this time. The final clinical study report will be written

based on these data. Any subjects who continue in the Follow-up Period will be discontinued from the study.

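### The protocol holds two unreconciled data cutoffs: an obsolete 36-month one for the primary and secondary endpoints, and a later one after all Month 24 visits

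*Protocol*

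**What the plan says.** The protocol gives two cutoffs.

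- **36 months.** The Abstract (Duration of study) says that "the data-cutoff for analysis of primary and secondary endpoints will be at 36 months from the time the study opens to accrual". Section 3.4.1 has the same sentence, and in both places it opens with the premise of an estimated 12-month accrual.
- **After all Month 24 visits.** The Abstract continues: "The Sponsor will establish a final clinical cutoff date after all subjects have completed the Month 24 Visit". Of the data held at that point it says: "The final clinical study report will be written based on these data". Section 11.2.2 repeats both statements.

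The Abstract also reports what happened to accrual: "the last patient was consented at 4 years and the final clinical cutoff is 2 years (24 months) after last patient was consented".

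The overall duration is inconsistent too. Section 3.1 says: "The total study duration is 6 years from the date of first subject enrolled". Section 3.4.2 says: "The study is estimated to reach completion 5 years from the time the study opens to accrual".

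The SAP gives no calendar cutoff and does not say which of the two governs the primary analysis.

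**The concern.** The 36-month cutoff is the only one that names the primary and secondary endpoints, and it falls a year before the last man was consented. The later cutoff is described as the basis of the final report, but nothing in the text withdraws the earlier one or makes it subordinate.

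If the 36-month sentence were applied, the FACT-P comparison would rest on early enrollees only and the stated power would not hold. The 24-month endpoints would suffer more, for example the proportion of men free of progression with recovered testosterone. The SAP also depends on the date: Table 1 censors men without PSA progression as of the time of analysis, and that time is not fixed. In an open-label trial, the date that governs the primary test should not be left to choice.

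**Working it through.** **1. Reproduce the timelines.** Last consent plus 24 months of follow-up:

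- estimated accrual: 12 + 24 = 36 months, which is the Abstract and Section 3.4.1 figure;
- reported accrual: 48 + 24 = 72 months = 6 years, which is the Abstract and Section 3.1 figure.

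So 36 months follows only from the 12-month accrual estimate. The 5 years in Section 3.4.2 fits neither sum. At 60 months, a man consented after month 60 − 24 = 36 would not have reached Month 24.

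**2. What follows without any accrual assumption.** At a 36-month cutoff:

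- a man consented after month 36 is not in the data;
- a man consented after month 36 − 12 = 24 has no Month 12 FACT-P;
- a man consented after month 36 − 24 = 12 has no 24-month endpoint.

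Screening between consent and Day 1 moves these limits slightly earlier.

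**3. Reproduce the stated power.** Inputs from protocol Section 11.1 (repeated in SAP 1.4): 27 evaluable per arm (30 × 0.9), difference 7.5, SD 8.7, two-sided 0.025. For a two-group t-test with n per arm, the noncentrality is (7.5/8.7) × √(n/2) on 2n − 2 degrees of freedom. At n = 27 this is 0.862 × √13.5 = 3.17, and power is 80.2%, matching the stated 80%.

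**4. Size of the loss at 36 months.** The documents give no accrual pattern. I assume the cumulative share enrolled by month t is (t/48)^k, so the share who have reached Month m is ((36 − m)/48)^k. Here k = 1 is uniform accrual; k = 0.5 (front-loaded) and k = 2 (back-loaded) serve as an illustrative range, not as bounds. Evaluable men per arm are the Month 12 count ÷ 3 × 0.9.

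| Accrual | Enrolled | Month 3 reached | Month 12 reached | Month 24 reached | Evaluable per arm | Superiority power |
|---|---|---|---|---|---|---|
| k = 0.5 | 77.9 | 74.6 | 63.6 | 45.0 | 19.1 | 63% |
| k = 1 | 67.5 | 61.9 | 45.0 | 22.5 | 13.5 | 45% |
| k = 2 | 50.6 | 42.5 | 22.5 | 5.6 | 6.75 | 20% |

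For k = 1 the noncentrality is 0.862 × √6.75 = 2.24 on 25 degrees of freedom, giving 45.5%.

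**5. Non-inferiority.** With margin 7, true difference 0 and 27 per arm, a one-sided 0.025 test gives 82.7%, close to the stated 82%. A two-sided 0.025 test, which is what the text specifies, gives 74.0%. That mismatch is a separate matter. At 13.5 per arm the two versions give 52% and 40%.

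**6. At the Section 11.2.2 cutoff.** Every man has passed Month 24, so the planned 27 evaluable per arm and the 80% power are unaffected.

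**The case against.** The strongest reply is that this is leftover wording with no practical effect.

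- The 36 months is tied to an estimated accrual that the same paragraph replaces.
- The next sentences of the Abstract set the later cutoff and base the final report on it.
- Section 11.2, which deals with cutoffs, contains no 36-month date.
- The SAP plans a sensitivity analysis of the primary endpoint with data up to 24 months, which fits a single late analysis.

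All of this stands, and it makes the later cutoff the more plausible intention. It does not remove the contradiction: the 36-month sentence remains current text in two places and is the only one that assigns a date to the primary and secondary endpoints.

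A reader might infer two stronger things that the documents do not support. The first is that the trial plans to analyse only about half its men. That would need the 36-month rule to override the final cutoff, and it would need uniform accrual, which is nowhere stated. Half would in any case describe only men with a Month 12 value: the MMRM also uses Month 3, which about 62 of 90 men would have reached under uniform accrual. The second is that the rule creates an unplanned efficacy look during randomisation. The Abstract reports last consent in the past tense, so month 36 had already passed when this version was written. Protocol Section 11.2.1 and SAP Section 3 also plan no interim efficacy analysis.

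**Conclusion.** The point holds as an internal contradiction. The 36-month cutoff is obsolete and conflicts with the reported accrual and with the final clinical cutoff. This much needs no assumption beyond the stated dates.

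The size is conditional on the 36-month rule being applied literally and on the accrual pattern. Under uniform accrual over 48 months, about 45 of 90 men would have Month 12 data (about 22 to 64 over the patterns tried) and about 22 would have Month 24 data. Superiority power would be about 45% (about 20% to 63%). These power figures use the plan's own t-test on men with a Month 12 value. The MMRM could recover a little from Month 3 data, but the documents give no correlation from which to quantify it.

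No loss arises if the Section 11.2.2 cutoff governs. The text should say that it does.

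**What to change.** - In the Abstract and Section 3.4.1, delete the 36-month cutoff and state that the primary and secondary endpoints are analysed at the final clinical cutoff of Section 11.2.2.
- In Section 3.4.2, change 5 years to 6, in line with the Abstract and Section 3.1.
- In the SAP, name the same cutoff as the analysis date for the primary and secondary endpoints, so that the censoring in Table 1 has a defined reference point.

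The cost is wording in two documents. No visits, patients or follow-up are added, because the final cutoff already waits for all Month 24 visits.
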